### **Hypotheses of the study:**

1. There will be no significant difference between scapular muscle strengthening and PNF exercise on improving muscle strength of upper trapezius in patients with shoulder impingement syndrome.

2. There will be no significant difference between scapular muscle strengthening and PNF exercise on improving muscle strength of middle trapezius in patients with shoulder impingement syndrome.
3. There will be no significant difference between scapular muscle strengthening and PNF exercise on improving muscle strength of lower trapezius in patients with shoulder impingement syndrome.
4. There will be no significant difference between scapular muscle strengthening and PNF exercise on improving muscle strength of serratus anterior in patients with shoulder impingement syndrome.
5. There will be no significant difference between scapular muscle strengthening and PNF exercise on muscle ratio of upper trapezius/lower trapezius muscles in patients with shoulder impingement syndrome.
6. There will be no significant difference between scapular muscle strengthening and PNF exercise on muscle ratio of upper trapezius/middle trapezius muscles in patients with shoulder impingement syndrome.
7. There will be no significant difference between scapular muscle strengthening and PNF exercise on muscle ratio of upper trapezius/serratus anterior muscles in patients with shoulder impingement syndrome.
8. There will be no significant difference between scapular muscle strengthening and PNF exercise on scapular symmetry at 0° abduction in patients with shoulder impingement syndrome.
9. There will be no significant difference between scapular muscle strengthening and motor control exercise on scapular symmetry at 45° abduction in patients with shoulder impingement syndrome.
10. There will be no significant difference between Scapular muscle strengthening and motor control exercise on scapular symmetry at 90° abduction in patients with shoulder impingement syndrome.

11. There will be no significant difference between scapular muscle strengthening and PNF exercise on improving pain in patients with shoulder impingement syndrome.
12. There will be no significant difference between scapular muscle strengthening and PNF exercise on improving function in patients with shoulder impingement syndrome.

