## Sample size calculation:

In order to detect an effect size of Cohen's  $d = 0.80$  with 80% power ( $\alpha = 0.05$ ), G\*power software (version 3.1.9.7; Franz Faul, Universitat Kiel, Germany) suggests we will need 64 participants, however, we will aim to recruit 66 subjects to have equal groups representation (22 per group) using analysis of variance (ANOVA) test as shown in the (figure 7).

[figure not shown]

Figure 1 ample size calculation

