## **Assessment procedure**

Assessment procedure will be performed before and after the treatment. The following procedure will be conducted

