## **2. Isometric strength imbalance of shoulder girdle muscles**

Isometric strength imbalance of shoulder girdle will be examined bilaterally. Based on the muscle test results from the previous measurement, The ratio of UT/SA and MR/LR will be calculated.

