**Figure 20 SCAPULAR ANTERIOR DEPRESSION**

## **Statistical analysis**

- Data will be analyzed using the statistical package for social science (SPSS) program, version 27 (SPSS Inc, Chicago, IL, USA).
- Descriptive statistics will be used to summarize the data. Data will be reported as mean  $\pm$  SD for quantitative variables and frequency distribution (%) for categorical variables.
- The normality of data will be checked using Shapiro–Wilk test.
- Levene’s test will be used to check the homogeneity between groups.
- Two-way Multiple Analysis of Variance (MANOVA) will be conducted to compare the mean values of the measured variables of the three groups.
- The level of significance for all statistical tests will be set at  $\alpha = 0.05$ .

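### The stated 80% power belongs to a single-outcome ANOVA with no outcome named; the planned analysis is a MANOVA of about twelve outcomes, whose power is unstated

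*Protocol*

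**What the plan says.** The Sample size calculation section takes Cohen's d = 0.80, 80% power and alpha 0.05, and reports that the software "suggests we will need 64 participants". The number is raised in order to "recruit 66 subjects to have equal groups representation (22 per group"), and the calculation is made "using analysis of variance (ANOVA) test as shown in the (figure 7"). The section names no outcome, and gives no number of outcomes, correlation between outcomes or multivariate effect size.

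The Statistical analysis section names one between-group analysis: "Two-way Multiple Analysis of Variance (MANOVA) will be conducted to compare the mean values of the measured variables of the three groups". It adds: "The level of significance for all statistical tests will be set at" 0.05. It does not list the variables, say what the second factor is, or mark any outcome as primary.

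The Hypotheses section lists twelve hypotheses, one per outcome: four muscle strengths, three strength ratios, scapular symmetry in three positions, pain, and function. The last reads "There will be no significant difference between scapular muscle strengthening and PNF exercise on improving function in patients with shoulder impingement syndrome". The strength-imbalance procedure has two ratios rather than three ("The ratio of UT/SA and MR/LR will be calculated"), so the count is eleven or twelve. On timing: "Assessment procedure will be performed before and after the treatment".

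**The concern.** A power figure is useful only if it describes the test that will be used to draw the conclusion. Here the sample size rests on an F test of one unnamed outcome, while the analysis section plans one multivariate test of about twelve outcomes. The two tests respond to different things. The ANOVA depends on the spread of three means on one scale. The MANOVA depends on how many outcomes differ, in which directions, and how the outcomes correlate, and the sample size section addresses none of these.

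The trial may therefore be reported as having had 80% power for its main analysis when nobody has calculated that power. This matters most for a null result, because the hypotheses are all worded as no difference between the two exercise programmes.

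**Working it through.** **1. Reproduce the protocol's figure.** Inputs from the Sample size calculation: d = 0.80, alpha 0.05, power 80%, three groups. Assumption: d was converted as f = d/2 = 0.40 (the software screenshot is not available). For a one-outcome ANOVA the noncentrality is λ = N·f², with 2 and N − 3 degrees of freedom.

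- N = 63: λ = 63 × 0.16 = 10.08, power 79.8%.
- N = 64: λ = 64 × 0.16 = 10.24, power 80.5%.
- N = 66: λ = 66 × 0.16 = 10.56, power 81.8%.

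So 64 is the smallest N reaching 80%. The sum is right, and it is the sum for one outcome.

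**2. What the MANOVA's power depends on.** With p outcomes at unit SD and equal correlation ρ, the multivariate signal is the squared distance δ′Σ⁻¹δ. With p = 12 and a difference d:

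- one outcome differs: d²(1 + 10ρ) / [(1 − ρ)(1 + 11ρ)]. This is d² at ρ = 0, 1.85d² at 0.5 and 3.07d² at 0.7;
- all twelve differ in the same direction: 12d² / (1 + 11ρ). This is 12d² at ρ = 0, 1.85d² at 0.5 and 1.38d² at 0.7.

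That signal is tested on 12 × 2 = 24 numerator degrees of freedom instead of 2. Correlation raises the signal in the first case and lowers it in the second.

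**3. Simulated MANOVA power at N = 66.** One-way MANOVA, Pillai trace, 22 per group, 12 outcomes, alpha 0.05. The correlations and the number of affected outcomes are assumptions. Checks: 5.3% rejection under the null, and 82.2% with a single outcome against the exact 81.8%. With f = 0.40 for each affected outcome, the value that reproduces 64:

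| Correlation | One affected | Three affected | All twelve affected |
|---|---|---|---|
| 0 | 28% | 81% | about 100% |
| 0.3 | 38% | 86% | 76% |
| 0.5 | 54% | 96% | 53% |
| 0.7 | 82% | over 99% | 40% |

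Taking 0.80 SD instead as the largest gap among the three means (either A and B 0.80 apart with C midway, or C 0.80 below A = B):

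- one affected: about 18–26% at correlation 0, rising to 59–76% at 0.7;
- three to six affected: 59% to nearly 100%;
- all affected: near 100% at correlation 0, falling to about 25–36% at 0.7.

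Repeat runs differ by a few points.

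**4. What a single-outcome test would have at N = 66.** f is the SD of the three group means divided by the within-group SD.

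- f = 0.40: 81.8%.
- Means 0.4, 0, −0.4: f² = (0.16 + 0 + 0.16)/3 = 0.1067, f = 0.327, λ = 7.04, power 63.6%.
- Means 0.8, 0.8, 0: deviations 0.267, 0.267, −0.533, f² = 0.1422, f = 0.377, λ = 9.39, power 76.8%.
- Strengthening against PNF alone, which is what the hypotheses compare: two-sided t test, 22 against 22, noncentrality 0.80 × √(22/2) = 2.65, power 73.6%.

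These figures assume that all 66 are analysed and make no use of the baseline value.

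**The case against.** The calculation contains no arithmetic error: 64 is correct for the test it describes. The hypotheses are also posed one outcome at a time, and an omnibus MANOVA alone cannot answer them. Univariate follow-up tests are therefore likely and may be set out in an analysis plan that is not shown. If they are run, single-outcome power is relevant. This stands in part: it makes the ANOVA figure useful for one step. It still does not make it the power of the MANOVA, and no outcome is named for it.

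The simulation is also not the planned analysis. It is one-way where the protocol says two-way, and it assumes equal correlations although the ratios are functions of the strengths. The same-direction pattern is also one choice among several: with half the effects reversed, the signal is 12d²/(1 − ρ), which at ρ = 0.5 is 24d² against 1.85d², or 13 times larger. All of this stands. The simulated range shows only that the power is undetermined.

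Two stronger readings are tempting, and the protocol supports neither.

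- A reader might infer that the MANOVA's power is far below 80% or that it would usually miss a single true difference. Several scenarios in the table lie close to 80% (76%, 81%, 82%) or above it.
- A reader might infer a greatly inflated false-positive rate, 46% for twelve independent tests at 0.05. That needs twelve separate tests not conditional on the MANOVA. The protocol does not describe such a procedure, and rules of that kind may sit in the analysis plan.

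**Conclusion.** The point holds as a mismatch between the sample size and the analysis. The 80% is the power of a one-outcome, three-group ANOVA with f = 0.40, and it cannot be quoted as the power of the planned MANOVA. That power is unstated and cannot be derived from the protocol. Under the assumptions shown it spans about 18% to nearly 100%, so no single corrected value can be put in its place.

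The 64% to 77% for a single-outcome ANOVA is a separate matter from the switch to MANOVA. It arises because f = d/2 is exact for two equal groups but not when 0.80 SD is the largest gap among three means. It belongs here only because any restated power must settle it.

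**What to change.** Name one primary outcome and one contrast of interest in both the Sample size calculation and the Statistical analysis sections. Analyse that outcome with a univariate model adjusted for its baseline value, which is already collected. Restate the power at N = 66 for that test, saying whether 0.80 is a gap between two arms or the basis of f = 0.40, and which SD it refers to. Without baseline adjustment the figure is 81.8% if f = 0.40, 64% to 77% if 0.80 SD is the largest gap among three means, and 73.6% for strengthening against PNF alone. Any gain from adjustment depends on a before–after correlation that the protocol does not give, so that correlation should be stated as an assumption. The other outcomes become secondary.

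Alternatively, keep the MANOVA as primary, list its outcomes (settling two ratios or three) and its second factor, state the assumed correlations and multivariate effect size, and give its power.

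The cost is protocol wording and one recalculation. No extra patients are required, but a figure of 64% to 77% is a material reduction from 80% and should be stated openly. Restoring 80% under that reading would need 71 to 94 participants, which is a separate decision for the sponsor.

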## Subjects:

Sixty-six male and female patients, with age between 20-50 years, diagnosed with SIS will be recruited through direct referrals, thus, a sample of convenience will be used. They will be asked to sign the informed consent

form (**Appendix I**). Participants will be randomly allocated to three experimental groups as follow:

**Group A** (n=22): will receive a program of scapular muscle strengthening exercises for 18 sessions (3 sessions per week for six weeks)

**Group B** (n=22): will receive a scapular PNF exercise program for the same frequency as in group A

**Group C** (n=22): will be a control group who will not receive any treatment during the study period.

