#### **Randomization:**

Patients will be randomly assigned into one of the three groups. We will use a simple randomization method to allocate participants to the groups. A random number generator available online from [www.randomization.com](http://www.randomization.com) will be used.

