### **1. Measuring isometric strength with HHD**

The HHD will be used to record the amount of resistance (in kilograms) applied by the examiner during the 4 scapular muscle tests as shown in **Figures 14 to 17**.

Muscle testing will be performed by first pre-positioning the scapula in the midrange position of scapular motion for the specific muscle test. The midrange position will be located by having the subject go through the available scapular range of motion, and then the midrange will be estimated as the midpoint of the motion.

This midrange position will be selected to optimize the length-tension relationship of the tested muscle and, therefore, the generation of a maximum isometric contraction (**Michener et al., 2005**).

The subjects will be instructed to maintain the midrange position during each muscle test as resistance was gradually applied via the HHD until the examiner matches the subject's effort (**Michener et al., 2005**).

The LT muscle test will be performed as described by Hislop et al. (**1995**) with the resistance force from the HHD being applied to the spine of the scapula

midway between the acromial process and the root of the spine, as shown in **Figure 14**.

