**Figure 11 Upper trapezius muscle test.**

All subjects will perform the muscle tests in the same order: LT, SA, MT, and UT muscle tests. The examiner will not view the digital readout on the HHD during performance of the muscle test. After the muscle test is completed, the examiner then will view the kilograms and recorded the information on a data recording sheet. Each muscle test will be performed 3 times consecutively, and the average will be used for data analysis.

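### Strength in kilograms is compared across a mixed-sex sample, with sex used in neither the allocation nor the stated comparison: an avoidable loss of precision whose size depends on how baseline is handled

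*Protocol*

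**What the plan says.** The Subjects section of the Protocol recruits one pooled sample: "Sixty-six male and female patients, with age between 20-50 years, diagnosed with SIS". It states no sex split.

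Under Measuring isometric strength with HHD, the scale is absolute force: "The HHD will be used to record the amount of resistance (in kilograms) applied by the examiner". At the end of that procedure, "Each muscle test will be performed 3 times consecutively, and the average will be used for data analysis". No scaling to body mass or to the other side is described for these values. They are the outcomes of hypotheses 1-4 (upper, middle and lower trapezius, and serratus anterior), each of which compares strengthening with PNF.

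The Randomization section states: "We will use a simple randomization method to allocate participants to the groups". It names no strata and no blocks.

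The Assessment procedure section states: "Assessment procedure will be performed before and after the treatment".

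The Statistical analysis section plans a two-way MANOVA "to compare the mean values of the measured variables of the three groups". It does not name the two factors, does not say whether time is a repeated measure, and mentions neither baseline nor sex.

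**The concern.** Sex is known for every patient before allocation and can be expected to predict absolute muscle force. If it is not used, two things can follow.

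- The male-female difference can sit in the error term of the strength comparisons and lower their power.
- In arms of 22, a chance difference in the share of men can shift the estimated strength difference in this particular trial.

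Four of the twelve hypotheses are concerned. There is little margin, because the sample size was set by a three-arm test at about 80% power and each of these hypotheses is a two-arm contrast.

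**Working it through.** **Inputs from the Protocol.** d = 0.80, alpha 0.05, 80% power, 64 patients raised to 66, 22 per arm (Sample size calculation). Reliability of the dynamometer (Hand-held dynamometer section): ICC .75-.99 in patients with impingement for all muscles except the upper trapezius, and .45-.65 for the upper trapezius in a sentence about healthy subjects.

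**Assumptions, not in the Protocol.** The male-female gap D is 0.5 to 2.0 within-sex SDs and the same before and after treatment. Half the patients are men. d = 0.80 is a within-sex effect.

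**1. The plan's own figure.** For a three-group one-way ANOVA with f = d/2 = 0.40 and noncentrality N × f², the smallest N with 80% power is 64 (power 0.805). At 66 it is 0.818. The stated figure reproduces. For the two-arm contrast of hypotheses 1-4, the noncentrality is 0.80 × √(22/2) = 2.65 on 42 df, and power is 0.736.

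**2. Raw post-treatment means compared.** The SD is inflated by √(1 + p(1−p)D²), which is √(1 + D²/4) at p = 0.5. The effective d is 0.80 divided by that factor.

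| D | SD factor | effective d | power, 22 v 22 | power, three-arm test, N = 66 |
|---|---|---|---|---|
| 0 | 1.00 | 0.80 | 0.74 | 0.82 |
| 0.5 | 1.03 | 0.78 | 0.71 | 0.79 |
| 1.0 | 1.12 | 0.72 | 0.64 | 0.72 |
| 1.5 | 1.25 | 0.64 | 0.55 | 0.62 |
| 2.0 | 1.41 | 0.57 | 0.45 | 0.51 |

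**3. Chance imbalance.** Take the stated 22 per arm and let the number of men in each active arm be Binomial(22, 0.5). The probability that the two differ by five or more is 0.174. Five men are 5/22 = 0.23 of an arm, so such a split shifts the raw mean difference by 0.23 within-sex SD at D = 1.0 and by 0.23 × 1.5 = 0.34 at D = 1.5.

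**4. Group-by-time test.** A constant offset D enters both the before and the after value and drops out of their difference. In a simulation with arm effects 0.8, 0.4 and 0 and a within-sex pre-post correlation of 0.5, power at D = 0, 1 and 2 was 0.63, 0.64 and 0.63. The post-only comparison gave 0.64, 0.54 and 0.36.

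**5. Baseline strength as a covariate.** Let b = D²/4, R the pooled pre-post correlation, and r = R(1+b) − b the within-sex one. Residual variance is (1+b)(1−R²) with baseline only, and 1−r² with baseline and sex. As a further assumption, the reliability figures stand in for R: 0.55 is mid-range for the upper trapezius, 0.75 is the lower end for the other muscles, and 0.90 is a high value. Power uses 0.80/√(residual variance) at 22 per arm and ignores the one or two degrees of freedom spent.

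| D | R | baseline only | baseline + sex | cut | power without → with sex |
|---|---|---|---|---|---|
| 1.0 | 0.55 | 0.872 | 0.809 | 7% | 0.79 → 0.82 |
| 1.0 | 0.75 | 0.547 | 0.527 | 4% | 0.94 → 0.95 |
| 1.0 | 0.90 | 0.237 | 0.234 | 1% | no material change |
| 1.5 | 0.55 | 1.090 | 0.912 | 16% | 0.70 → 0.77 |
| 1.5 | 0.75 | 0.684 | 0.629 | 8% | 0.88 → 0.90 |
| 1.5 | 0.90 | 0.297 | 0.288 | 3% | no material change |

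**6. Type I error.** With no treatment effect, the simulated rejection rate for the post-only, post-plus-sex, change and baseline-adjusted analyses was between 0.04 and 0.06 at D = 0, 1 and 2. With 3,000 replicates the Monte Carlo standard error is √(0.05 × 0.95/3000) = 0.004.

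**The case against.** The strongest reply is that the large losses in step 2 belong to an analysis that the Protocol does not clearly state. It plans a two-way MANOVA, its hypotheses speak of improvement, and it measures before and after treatment, so time is the natural second factor. In a proper group-by-time test the sex offset cancels. This stands as a limit on the size. It does not remove the point, because the Statistical analysis section names neither the second factor nor a repeated measure, and its wording describes a comparison of group means.

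Three further replies also stand.

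- The low reliability figure covers the upper trapezius only. For the other three muscles baseline is a better proxy, and sex adds little once it is in the model.
- The Protocol does not say that d = 0.80 is within-sex. If it was standardized on the mixed population, nothing planned is lost, and using sex is a gain forgone.
- The choice of covariates is commonly left to a SAP, which is not at hand here. The missing covariate alone would not be a finding. The allocation method is different: the Protocol fixes it, and no later SAP can repair it.

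A reader might infer that a sex imbalance would make the strength tests invalid, or could manufacture a finding beyond the stated error rate. The documents do not support this. Allocation is random, chance imbalance is already covered by alpha, and the simulated type I error stays near 0.05.

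**Conclusion.** The point holds as one of precision. The plan uses a mixed-sex sample, outcomes in absolute kilograms, simple randomization and no use of sex.

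The size depends on the analysis. For raw post-treatment means, two-arm power falls from 74% to 71-45% over the assumed gaps. For a group-by-time test, a constant gap costs nothing. For a baseline-adjusted model, adding sex cuts residual variance by about 1-16% over gaps of 1.0-1.5 SD and correlations of 0.90-0.55, and matters most for the upper trapezius.

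It would be tempting to present the 45% figure as the trial's power. It rests on the largest assumed gap, an even sex split, a within-sex d and a post-only comparison, and the Protocol establishes none of these. This is a worthwhile low-cost improvement, at most a mild recommendation.

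**What to change.** In Statistical analysis, state that each of the four strength outcomes is compared between groups with baseline strength and sex as covariates. In Randomization, replace simple randomization with a permuted-block list stratified by sex.

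The blocks are essential. Separate lists for men and women, each still filled by simple randomization, leave the sex balance as it was. Blocks also help secure the stated group size ("22 per group) using analysis of variance (ANOVA) test"). If each of 66 patients is allocated independently with probability 1/3, the exact 22/22/22 split has probability 66!/(22!³ × 3⁶⁶) = 0.012.

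The cost is one or two degrees of freedom and a two-stratum blocked list, with no new data or patients. Blocking makes allocation slightly more predictable, and concealed, varying block sizes limit that. The list must be in place before the first patient is randomized.

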### **Purpose of the study:**

The purpose of this study is to compare the effect of scapular muscle strengthening versus PNF exercise on scapular muscle strength, scapular muscles ratio, scapular asymmetry, pain, and function in patients with shoulder impingement syndrome.

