### **Research question:**

What is/are the effect(s) of scapular muscle strengthening compared to PNF exercise on isometric scapular muscle strength, scapular muscles ratio and scapular asymmetry in patients with shoulder impingent syndrome.

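### The stated hypotheses compare only strengthening with PNF, but the trial is designed, sized and analysed with an untreated third arm, and the three-group test named does not answer those hypotheses

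*Protocol*

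**What the plan says.** - **Aims.** Under Purpose of the study: "The purpose of this study is to compare the effect of scapular muscle strengthening versus PNF exercise on scapular muscle strength", followed by the other outcomes. The opening of Chapter III repeats this aim. The Research question asks about the "effect(s) of scapular muscle strengthening compared to PNF exercise on isometric scapular muscle strength", again with further outcomes.
- **Hypotheses.** All twelve items under Hypotheses of the study set one exercise programme against the other. For pain: "There will be no significant difference between scapular muscle strengthening and PNF exercise on improving pain in patients with shoulder impingement syndrome". For function: "There will be no significant difference between scapular muscle strengthening and PNF exercise on improving function in patients with shoulder impingement syndrome". Items 9 and 10 call the comparator motor control exercise instead of PNF. No item names the control group.
- **Design.** Under Randomization: "Patients will be randomly assigned into one of the three groups". Under Subjects, each group has 22 patients, and Group C "will be a control group who will not receive any treatment during the study period". Treatment procedure repeats this.
- **Sizing.** Sample size calculation uses an ANOVA with Cohen's d = 0.80, 80% power and alpha 0.05. It arrives at 64, raised to 66 for three equal groups.
- **Analysis.** Under Statistical analysis, a two-way MANOVA "will be conducted to compare the mean values of the measured variables of the three groups". No pairwise comparison is named there. "The level of significance for all statistical tests will be set at" 0.05.

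**The concern.** The aims and hypotheses describe a two-arm question, while the design, sizing and analysis describe a three-arm one. The protocol does not say how one answers the other.

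This matters because every hypothesis is worded as no significant difference between the programmes, so a null result is one the protocol itself anticipates. Several hypotheses also speak of improving strength, pain or function. Assessments take place only before and after treatment, so a change within either exercise group mixes treatment effect with natural recovery. Group C is the only part of the design that can separate the two, and no hypothesis draws on it.

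Two misreadings are open. A significant three-group result could be reported as a difference between the programmes when it comes from Group C. A null difference between the programmes could be reported as both working when neither does.

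**Working it through.** **Inputs.** Three groups of 22, d = 0.80, power 80% and alpha 0.05, all from Sample size calculation and Subjects. Assumptions: one outcome, common SD of 1, no dropout, no baseline adjustment, two-sided contrasts. A is strengthening, B is PNF, C is no treatment.

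**1. The plan's own figure.** Take a three-group omnibus F test with f = d/2 = 0.40 and noncentrality λ = N·f², on 2 and N − 3 degrees of freedom. The conversion is an assumption, because the software figure is not shown.
- N = 63: power 0.798
- N = 64: power 0.805
- N = 66: power 0.818

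So 64 is the smallest N reaching 80%, exactly as stated. A two-sample t test at d = 0.80 would need 26 per arm, 52 in all. The sizing therefore counts Group C, and its 80% belongs to the three-group test, not to A versus B.

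**2. What the three-group test can distinguish.** With equal groups, f² is the mean squared deviation of the three group means from their average.
- Both programmes work: means (0.80, 0.80, 0), f² = 0.64 × (1/3) × (2/3) = 0.1422
- Only strengthening works: means (0.80, 0, 0), f² = 0.64 × (1/3) × (2/3) = 0.1422

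In both cases f = 0.377 and λ = 66 × 0.1422 = 9.39, so power is 0.768. By symmetry it is the same if only PNF works. In the first case the A-versus-B hypothesis is true, yet the named test is significant about 77% of the time. In the second that hypothesis is false, and the rate is identical.

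**3. What A versus B alone can distinguish.** If both programmes work equally, or neither works, the A − B difference is zero. The contrast is then significant 5% of the time in either case, so a null result does not tell the two apart. Its precision is also limited: the 95% half-width is 2.018 × √(2/22) = 0.61 SD (42 degrees of freedom).

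**4. Power of the pairwise contrasts.** At d = 0.80 and 22 per arm, the noncentrality is 0.80 × √(22/2) = 2.65.

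| Comparison | Power |
|---|---|
| One contrast, unadjusted 0.05 | 0.736 (0.743 with pooled error, 63 df) |
| One contrast, Bonferroni 0.05/3, pooled error | 0.579 |
| Both A and B beat C, unadjusted (simulation) | about 0.60 |

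Eighty per cent power per contrast at 0.05/3 would need 34 per arm, 102 in all.

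**The case against.** A reader might infer that the plan has no test involving Group C at all. The documents do not support that. The MANOVA compares all three groups and the sample size counts all three. If neither programme works, the omnibus test is significant about 5% of the time; if both work by d = 0.80, about 77%. So it carries some information about whether anything differs from no treatment. That part of the objection stands. What the test does not do is say which arms differ.

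It can also be said that follow-up contrasts and their multiplicity rule usually belong in a statistical analysis plan, which is not shown here. That is fair, and their absence alone is not the point. But purpose, question and hypotheses belong in the protocol. This protocol states them in full, and they do not match the three-group test it names.

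Finally, an untreated arm beside two active arms is a standard way to separate treatment effect from natural recovery. A reader might conclude that the arm is wasted and that its patients should move to A and B. The arm is not a design error; the gap is that no stated question uses it. Shrinking it is only a trade-off: at 26:26:14, A-versus-B power rises to 0.81, but A-versus-C power falls to 0.65.

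**Conclusion.** The point holds as a mismatch: two-arm aims and hypotheses against a three-arm design, sizing and analysis, with 22 of 66 patients (33%) in an arm that no hypothesis uses. Taken literally, the only between-group test named can give a wrong answer to the stated hypotheses. It would be significant about 77% of the time on one outcome when the programmes are equal and both beat no treatment by d = 0.80.

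The figures rest on the assumptions listed with the inputs. The planned MANOVA covers several outcomes, so 77% illustrates the problem and is not the power of the actual analysis. The protocol does not say that d = 0.80 is the strengthening-versus-PNF difference; it is used here for each contrast for want of another figure.

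A reader might also infer that the programmes could be called similarly effective once each beats Group C. That does not follow. No equivalence margin is stated, and the interval for A − B extends about 0.61 SD either side.

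**What to change.** 1. In Purpose of the study (and its repeat at the start of Chapter III), Research question and Hypotheses of the study, add strengthening versus no treatment and PNF versus no treatment, on pain and function.
2. In Statistical analysis, state that the hypotheses are answered by the A–B, A–C and B–C contrasts and not by the omnibus test, with A–B ranked first. State the multiplicity rule, and make clear that the ranking is not a gate; otherwise a null A–B result would block the two control contrasts just when they are needed.
3. State the reading rules. A programme is called effective only if it beats Group C. A non-significant A–B difference is not evidence of similar effect. The A–B difference is reported with its 95% interval.

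**Cost.** Wording only, with no added patients or measurements provided Group C is assessed at the same two times as the other groups. The downside is more stated comparisons at modest power: about 74% each at d = 0.80 unadjusted, 58% with Bonferroni over three, and about 60% for both programmes beating no treatment. The changes should be made before any results are seen, so that comparisons with Group C do not appear chosen afterwards.
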